9.2. Adverse Events

Investigators are responsible for monitoring the safety of patients who have entered this study and for alerting Lilly or its designee to any event that seems unusual, even if this event may be considered an unanticipated benefit to the patient.

The investigator is responsible for the appropriate medical care of patients during the study.

Investigators must document their review of each laboratory safety report.

The investigator remains responsible for following, through an appropriate health care option, AEs that are serious or otherwise medically important, considered related to the investigational product or the study, or that caused the patient to discontinue the investigational product before completing the study. The patient should be followed until the event resolves, stabilizes with appropriate diagnostic evaluation, or is reasonably explained. The frequency of follow-up evaluations of the AE is left to the discretion of the investigator.

Lack of drug effect is not an AE in clinical studies, because the purpose of the clinical study is to establish treatment effect.

After the ICF is signed, study site personnel will record via eCRF the occurrence and nature of each patient's preexisting conditions, including clinically significant signs and symptoms of the disease under treatment in the study. In addition, site personnel will record any change in the condition(s) and any new conditions as AEs. Investigators should record the following via the eCRF for each AE: time of onset, time of termination, severity and their assessment of the potential relatedness of each AE to protocol procedure or investigational product.

The investigator will interpret and document whether or not an AE has a reasonable possibility of being related to study treatment, or a study procedure, taking into account the disease, concomitant treatment or pathologies.

A "reasonable possibility" means that there is a cause and effect relationship between the investigational product and/or study procedure and the AE.

The investigator answers yes/no when making this assessment.

Planned surgeries and nonsurgical interventions should not be reported as AEs unless the underlying medical condition has worsened during the course of the study.

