9.2.1. Serious Adverse Events

An SAE is any AE from this study that results in one of the following outcomes:

- death
- initial or prolonged inpatient hospitalization
- a life-threatening experience (that is, immediate risk of dying)
- persistent or significant disability/incapacity
- congenital anomaly/birth defect
- important medical events that may not be immediately life-threatening or result in death or hospitalization but may jeopardize the patient or may require intervention to prevent one of the other outcomes listed in the definition above.
- All AEs occurring after signing the ICF are recorded in the eCRF and assessed for serious criteria. The SAE reporting to the sponsor begins after the patient has signed the ICF and has received investigational product. However, if an SAE occurs after signing the ICF, but prior to receiving investigational product, the SAE should be reported to the sponsor as per SAE-reporting requirements and timelines (Section 9.2) if it is considered reasonably possibly related to study procedure.

Study site personnel must alert Lilly or its designee of any SAE within 24 hours of investigator awareness of the event via a paper SAE form. If alerts are issued via telephone, they are to be immediately followed with official notification on study specific SAE forms. The SAE form should be completed by the investigator, and submitted via fax to the Sponsor's global patient safety department. This form includes a fax cover page that is prepopulated with the appropriate fax number. The 24-hour notification requirement refers to the initial SAE information and all follow-up SAE information. Patients with a serious hepatic AE should have additional data collected using the eCRF.

Pregnancy (during maternal or paternal exposure to investigational product) does not meet the definition of an AE. However, to fulfill regulatory requirements any pregnancy should be reported following the SAE process to collect data on the outcome for both mother and fetus.

Investigators are not obligated to actively seek AEs or SAEs in subjects once they have discontinued and/or completed the study (the patient disposition eCRF has been completed). However, if the investigator learns of any SAE, including a death, at any time after a subject has

been discharged from the study, and he or she considers the event reasonably possibly related to the study treatment or study participation, the investigator must promptly notify Lilly.

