9.2.1.1. Suspected Unexpected Serious Adverse Reactions

Suspected unexpected serious adverse reactions (SUSARs) are serious events that are not listed in the IB and that the investigator identifies as related to investigational product or procedure. United States 21 CFR 312.32 and European Union Clinical Trial Directive 2001/20/EC and the associated detailed guidances or national regulatory requirements in participating countries require the reporting of SUSARs. Lilly has procedures that will be followed for the identification, recording and expedited reporting of SUSARs that are consistent with global regulations and the associated detailed guidances.

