9.4.8. Safety Monitoring

Lilly will periodically review evolving aggregate safety data within the study by appropriate methods.

The Lilly designated medical monitor will monitor safety data throughout the course of the study. Lilly will review SAEs within time frames mandated by company procedures. The Lilly designated medical monitor will, as is appropriate, consult with the functionally independent Global Patient Safety therapeutic area physician or clinical scientist and periodically review trends in safety data and laboratory analytes. Any concerning trends in frequency or severity noted by an investigator and/or Lilly (or designee) may require further evaluation.

All deaths and SAE reports will be reviewed in a blinded manner by Lilly during the clinical trial. These reports will be reviewed to ensure completeness and accuracy, but will not be unblinded to Lilly during the clinical study. If a death or a clinical AE is deemed serious, unexpected, and possibly related to investigational product, only Lilly Global Patient Safety will be unblinded for regulatory reporting and safety monitoring purposes. These measures will

preserve the integrity of the data collected during this trial and minimize any potential for bias while providing for appropriate safety monitoring.

Investigators will monitor vital signs and carefully review findings that may be associated with cardiovascular events. Adverse event reports and vital signs will be collected at each study visit.

The cardiovascular monitoring plan includes the following:

- Regular monitoring of lipid levels
- Potential MACE (cardiovascular death, myocardial infarction, and stroke), other cardiovascular events (such as hospitalization for unstable angina, hospitalization for heart failure, serious arrhythmia, resuscitated sudden death, cardiogenic shock, and coronary interventions), and noncardiovascular deaths will be identified by the investigative site or through medical review and will be sent to a blinded Clinical Event Committee for adjudication at regular intervals.

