9.4.8.2. Data Monitoring Committee

A DMC will oversee the conduct of this study. The DMC will consist of members external to Lilly. This DMC will be guided by the DMC charter. At a minimum the DMC will include the following who have previous DMC experience:

- a specialist with expertise in hepatology and
- a statistician.

The DMC will review and evaluate data from the 12 week treatment period from patients in Cohort A.

In addition, the DMC may be convened if 2 or more patients permanently discontinue due to safety. The DMC chair will determine if the full DMC needs to convene.

The DMC chair will have access to all SAEs as reported to regulatory authorities and may convene a meeting at any time.

Access to the unblinded interim data will be limited to the statisticians who conduct the interim analyses and the DMC. The statisticians conducting the interim analyses will be independent from the study team. The study team will not have access to the unblinded data.

Data that the DMC will review include, but are not limited to, reasons for study discontinuation, AEs including SAEs, clinical laboratory data and vital signs. The DMC may recommend continuation of the study as designed, temporary suspension of enrollment, or discontinuation of a particular dose regimen or discontinuation of the entire study. The DMC may request to review efficacy data to investigate the benefit/risk relationship in the context of safety

observations for ongoing patients in the study. Details of the DMC and interim safety analyses will be documented in a DMC charter.

In addition to the DMC members, a limited number of prespecified individuals may gain access to the unblinded PK, safety, and efficacy data (as specified in the unblinding plan) prior to the final database lock to initiate the exploration and/or final population of the PK/PD model development processes. Information that may unblind the study during the analyses will not be reported to study sites or the blinded study team until the database is locked.

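### Protocol 9.2 defines a reasonable possibility of relatedness as actual cause and effect, which is stricter than the term itself and than the possibility wording in 9.2.1 and 9.4.8

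*Protocol*

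**What the plan says.** Protocol 9.2 (Adverse Events) has the investigator decide "whether or not an AE has a reasonable possibility of being related to study treatment, or a study procedure", weighing the disease and other treatment. The next sentence says that a reasonable possibility "means that there is a cause and effect relationship between the investigational product and/or study procedure and the AE". The response is binary: "The investigator answers yes/no when making this assessment".

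Other sections rely on a relatedness judgement:

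- **9.2.1 (Serious Adverse Events).** An SAE after consent but before dosing goes through SAE reporting "if it is considered reasonably possibly related to study procedure". An SAE that the investigator learns of after the patient has left the study must be notified only on a similar judgement about treatment or participation.
- **9.2.1.1 (SUSARs).** These are "serious events that are not listed in the IB and that the investigator identifies as related to investigational product or procedure".
- **9.4.8 (Safety Monitoring).** The sponsor's safety group is unblinded when a death or clinical event "is deemed serious, unexpected, and possibly related to investigational product". The section does not say who makes that judgement.
- **9.4.8.2 (Data Monitoring Committee).** "The DMC chair will have access to all SAEs as reported to regulatory authorities and may convene a meeting at any time". The scheduled DMC review is of Cohort A.

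**The concern.** The definition drops the possibility element from the term it defines. It contains no 'may', no 'suggests' and no 'cannot be excluded', and there is no middle answer. An investigator who thinks that the drug might have caused an event, but cannot say that it did, is told by the question to answer 'yes' and by the definition to answer 'no'.

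The gap is easiest to see for a serious hepatic event. Section 3.3 names hepatotoxicity as an important potential risk, every patient has a cholestatic liver disease, and investigators are blinded. Such an event may readily be thought possibly related while cause and effect stays unestablished.

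At stake is whether some serious events are notified to the sponsor at all, and whether others are classed as SUSARs.

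**Working it through.** The point involves no figure, so the check sets the texts side by side and follows the relatedness call through each reporting route.

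**Step 1: the standards compared**

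| Place in protocol | Standard |
|---|---|
| 9.2, eCRF recording instruction | potential relatedness |
| 9.2, question to the investigator | reasonable possibility |
| 9.2, definition of that term | a cause-and-effect relationship exists |
| 9.2.1, pre-dose and post-discharge SAEs | reasonably possible relation |
| 9.2.1.1, SUSAR | related, in the investigator's judgement; no standard given |
| 9.4.8, unblinding of the safety group | possible relation |

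Of the four places that set a standard besides the definition, all use possibility wording. Section 9.2.1.1 sets none. The definition is therefore the outlier, including against its own term.

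**Step 2: routes that depend on the call**

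- *Post-discharge SAEs (9.2.1).* The duty to notify rests on the investigator's relatedness judgement. The protocol describes no other route by which the sponsor would learn of the event. This is the firmest consequence.
- *Pre-dose SAEs (9.2.1).* These are reported as SAEs only if judged possibly related to a study procedure. The event is still recorded as an AE in the eCRF, so it is not lost, but it may not be handled as an SAE report.
- *SUSARs (9.2.1.1).* The stated definition turns on the investigator's call.
- *DMC chair's ongoing access (9.4.8.2).* This covers SAEs in the form reported to regulators, so it could be affected indirectly.

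Section 9.2.1 uses possibility wording of its own, but the only elaboration of what such wording means is the sentence in 9.2. That is how the strict reading could carry over.

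**Step 3: routes that do not depend on the call**

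- Sites notify the sponsor of SAEs after dosing within 24 hours, whatever the causality answer (9.2.1).
- The sponsor reviews all deaths and SAE reports blinded (9.4.8).
- The DMC's Cohort A review covers AEs and SAEs without a causality filter (9.4.8.2; SAP 6.16.1).
- Follow-up of an AE is required if it is serious or otherwise medically important, or related, or led to stopping the product (9.2). Serious events are therefore followed either way.
- The planned TEAE and SAE tables (SAP 6.13.2) are not restricted to related events.

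**Step 4: Cohort B**

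Cohort B randomizes 20 patients to 4 mg and 12 to placebo, 20 + 12 = 32 in all. The scheduled DMC review concerns Cohort A, and Protocol 10.3.7 plans no further interim analysis. During Cohort B the DMC prompts set out in the protocol are the chair's access to reported SAEs, the chair's freedom to call a meeting, and possible convening after 2 or more permanent discontinuations for safety. Only the first can be narrowed by the definition, and only if regulatory reporting itself is narrowed.

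**The case against.** A reader might infer that under-called SAEs drop out of expedited reporting and out of the DMC chair's sight. The documents do not support that. On-treatment SAEs reach the sponsor and are reviewed there. Section 9.2.1.1 refers to sponsor procedures for identifying SUSARs, which are not reproduced, and 9.4.8 does not name the investigator as the person who judges relatedness. A sponsor causality assessment is neither described nor ruled out, so it cannot be said that each 'no' is one SUSAR not expedited. The chair's access is not expressly limited to SUSARs, the chair may call a meeting at any time, and further DMC detail sits in a charter outside these documents.

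Nor can 9.4.8 be counted twice. If its looser wording conflicts with the 9.2 definition, it cannot also be treated as governed by that definition.

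Several protections do not use the definition at all: adjudication of potential MACE and of suspected DVT or PE, hepatic data collection on laboratory triggers, and the sponsor's aggregate safety review.

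Finally, a literal reading is not certain. The surrounding text points toward possibility, and nothing in the documents shows how often a site would apply the stricter sentence.

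All of this stands, and it limits the consequence. It does not remove the contradiction within 9.2, and it gives no backup for a post-discharge event that the sponsor never receives.

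**Conclusion.** The definition in 9.2 is wrong as written: followed literally, it gives a stricter answer than the question it is meant to explain. Its direct reach is limited to post-discharge SAEs, pre-dose procedure-related SAEs, and the investigator's call within the SUSAR definition.

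A delay or omission in expedited reporting, or in the chair's ongoing view of such SAEs, is conditional on two assumptions: that investigators apply the sentence literally, and that the sponsor makes no causality assessment of its own. If both held, the gap would matter mainly in Cohort B, where no DMC data review is scheduled.

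The documents give neither an event rate nor a rate of misreading, so the number of events cannot be estimated. No efficacy estimate and no planned safety table changes. This is a wording inconsistency in a safety-reporting rule, small in likely extent and easy to remove.

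**What to change.** Reword the sentence in 9.2 as a possibility standard, for example: 'A reasonable possibility means that there is evidence or a plausible argument that the investigational product or a study procedure may have caused the AE; an established cause-and-effect relationship is not required.' Apply the same standard to the word 'related' in 9.2.1.1. Sections 9.2.1 and 9.4.8 already use possibility wording and need no change.

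An optional addition is a statement of whether the sponsor's own causality assessment can make an event a SUSAR. That would settle the open assumption above.

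The cost is one protocol sentence, the matching reference in 9.2.1.1 and a line in site training. Slightly more events would be classed as related.

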9.2.1. Serious Adverse Events

An SAE is any AE from this study that results in one of the following outcomes:

- death
- initial or prolonged inpatient hospitalization
- a life-threatening experience (that is, immediate risk of dying)
- persistent or significant disability/incapacity
- congenital anomaly/birth defect
- important medical events that may not be immediately life-threatening or result in death or hospitalization but may jeopardize the patient or may require intervention to prevent one of the other outcomes listed in the definition above.
- All AEs occurring after signing the ICF are recorded in the eCRF and assessed for serious criteria. The SAE reporting to the sponsor begins after the patient has signed the ICF and has received investigational product. However, if an SAE occurs after signing the ICF, but prior to receiving investigational product, the SAE should be reported to the sponsor as per SAE-reporting requirements and timelines (Section 9.2) if it is considered reasonably possibly related to study procedure.

Study site personnel must alert Lilly or its designee of any SAE within 24 hours of investigator awareness of the event via a paper SAE form. If alerts are issued via telephone, they are to be immediately followed with official notification on study specific SAE forms. The SAE form should be completed by the investigator, and submitted via fax to the Sponsor's global patient safety department. This form includes a fax cover page that is prepopulated with the appropriate fax number. The 24-hour notification requirement refers to the initial SAE information and all follow-up SAE information. Patients with a serious hepatic AE should have additional data collected using the eCRF.

Pregnancy (during maternal or paternal exposure to investigational product) does not meet the definition of an AE. However, to fulfill regulatory requirements any pregnancy should be reported following the SAE process to collect data on the outcome for both mother and fetus.

Investigators are not obligated to actively seek AEs or SAEs in subjects once they have discontinued and/or completed the study (the patient disposition eCRF has been completed). However, if the investigator learns of any SAE, including a death, at any time after a subject has

been discharged from the study, and he or she considers the event reasonably possibly related to the study treatment or study participation, the investigator must promptly notify Lilly.

9.2.1.1. Suspected Unexpected Serious Adverse Reactions

Suspected unexpected serious adverse reactions (SUSARs) are serious events that are not listed in the IB and that the investigator identifies as related to investigational product or procedure. United States 21 CFR 312.32 and European Union Clinical Trial Directive 2001/20/EC and the associated detailed guidances or national regulatory requirements in participating countries require the reporting of SUSARs. Lilly has procedures that will be followed for the identification, recording and expedited reporting of SUSARs that are consistent with global regulations and the associated detailed guidances.

9.2.2. Adverse Events of Special Interest

Adverse events of special interest will include the following:

- Infections (including TB, herpes zoster, or opportunistic infections)
- Malignancies
- Hepatic events (Section 9.4.7)
- Major adverse cardiovascular events (MACE) (Section 9.4.8)
- Arterial thrombotic events
- Thrombotic events (DVT and PE) (Section 9.4.8.1).

Sites will provide details on these AEs as instructed on the eCRF and may be asked for additional description by Lilly.

9.2.3. Complaint Handling

Lilly collects product complaints on investigational products and drug delivery systems used in clinical studies in order to ensure the safety of study participants, monitor quality, and to facilitate process and product improvements.

Patients will be instructed to contact the investigator as soon as possible if he or she has a complaint or problem with the investigational product so that the situation can be assessed.

9.3. Treatment of Overdose

Refer to the IB.

9.4. Safety

9.4.1. Electrocardiograms

A single 12-lead standard ECG will be obtained locally at Visit 1 and read by a qualified physician (the investigator or qualified designee) at the site to determine whether the patient meets entry criteria.

Electrocardiograms may be obtained at additional times, when deemed clinically necessary.

9.4.2. Vital Signs

For each patient, vital signs measurements should be conducted according to the Schedule of Activities (Section 2). Subjects should be seated and relaxed with both feet on the floor for at least 5 minutes prior to taking measurements.

Three replicate blood pressure readings should be made at each time point at approximately 30- to 60-second intervals. A single-pulse measurement should be taken simultaneously with at least one of the blood pressure readings. Blood pressure and pulse measurements should be made using either automated or manual equipment. If measurements are machine averaged, the average blood pressure reading should be recorded on the CRF. If measurements are manual or the machine does not provide an average reading, then each individual reading should be recorded on the CRF. Measurements should be made before any scheduled blood draws.

Additional measurements of vital signs may be performed at the discretion of the investigator.

Any clinically significant findings from vital signs measurement that result in a diagnosis and that occur after the patient receives the first dose of study treatment should be reported to Lilly or its designee as an AE via eCRF.

9.4.3. Physical Examination

For each patient, physical examinations will be conducted according to the Schedule of Activities (Section 2). One complete physical examination (excluding pelvic and rectal examinations) will be performed at Visit 1 (Screening). All remaining physical examinations throughout the study should include a symptom-directed physical examination. A complete physical examination may be repeated at the investigator's discretion at any time a patient presents with physical complaints.

